3.2. Exclusion Criteria for Enrollment

Participants who meet any of the following criteria will not be eligible for participation

- 1. Is anticipated to require ICU admission for mechanical ventilation within 24 hours of enrollment.
- 2. Requires more than 6 liters/minute of oxygen to maintain O₂ saturation above 95%.
- 3. Is not expected to survive longer than 24 hours.

Version: 7.0

- 4. Has a platelet count less than 100,000/μL, hemoglobin <9 g/dL, or has a disorder of the hematologic system including anemic disorder or other blood dyscrasia, cancer of the hematologic system, history of bone marrow transplant, or other significant hematologic disease.
- 5. Women who are pregnant or breastfeeding.
- 6. Is experiencing DAIDS AE grading scale grade 4 baseline medical conditions or laboratory abnormalities.
- 7. Has received a vaccine for COVID-19 prior to enrollment, or plans to receive a vaccine for COVID-19 before the end-of-study visit.
- 8. Has received an experimental antiviral treatment for COVID-19 prior to enrollment.
- 9. Has received convalescent plasma or other monoclonal antibodies prior to enrollment.
- 10. Is participating in another clinical study that involves pharmacologic intervention or has participated in another study within 30 days of 5 half-lives of the investigational agent (observational study participation is permitted).
- 11. In the opinion of the investigator, has end-organ disease as a result of relevant comorbidities: chronic kidney disease (reduced glomerular filtration rate [GFR] <30 mL/min by the Modification of Diet in Renal Disease (MDRD) study equation prior to COVID-19 symptom onset), decompensated chronic liver disease or cirrhosis, decompensated congestive heart failure, active peripheral vascular disease including active diabetic ulcers, chronic pulmonary disease prior to COVID-19 symptom onset requiring bilevel positive airway pressure (BiPAP) or >4 L/min supplemental oxygen at baseline; if using ≤4 L/min supplemental oxygen at baseline, consultation with and approval of the sponsor is required prior to enrollment.
- 12. Has a diagnosis of cancer that is not in remission. Noninvasive cancers, such as basal and squamous cell carcinoma or history of in situ tumors are allowed at the discretion of the investigator after discussion with the sponsor.
- 13. Has received an organ transplantation.
- 14. Has received a bone marrow transplantation.
- 15. Has been on immunosuppressive medications within 1 month prior to enrollment.
- 16. Has any condition that would, in the opinion of the investigator, put the participant at increased risk for participation in a clinical trial.
- 17. Has known active hepatitis C (HCV RNA positive), active hepatitis B (hepatitis B surface antigen positive), or HIV (ELISA and confirmatory Western blotting). New screening tests not required.
- 18. Is currently taking nucleos(t)ide analogues for HIV or hepatitis B, or for their prevention, within 30 days of study enrollment.
- 19. Is currently taking systemic corticosteroids other than replacement doses or for treatment of COVID-19.
- 20. Has a body mass index (BMI) >50 kg/m².
- 21. Is anticipated to require surgery within 48 hours after hospital admission.

Version: 7.0

22. Is anticipated to have an NPO (nothing per mouth) order placed within 48 hours after hospital admission that is expected to last for ≥24 hours.

4. INVESTIGATIONAL PLAN

4.1. Definitions

- I. Enrolled: From time consented to initiation of study drug until designated as off study either through discontinuation or completion of the study.
- II. Randomized: when a patient identification (ID) number is assigned through randomization.
- III. Screen Failures: signed informed consent, but then determined to be ineligible or withdraws before initiation of study drug.
- IV. Discontinued: randomized, but then withdrawn by investigator or withdraws consent.
- V. Completed: Participants are considered completed when they are followed through to Day 28 or died before that.

4.2. Randomization and Blinding

This study will be conducted in up to 4 parts. During Part 1, participants will be randomized in a 1:1:1 ratio to EIDD-2801 200 mg BID, EIDD-2801 400 mg BID, or placebo BID; during Part 2, approximately 21 participants will be randomized in a 2:1 ratio to EIDD-2801 400 mg BID:placebo BID; during Part 3, approximately 21 participants will be randomized in a 2:1 ratio to EIDD-2801 800 mg BID:placebo BID. An optional Part 4 may be added during which approximately 21 participants will be randomized in a 2:1 ratio to EIDD-2801 BID:placebo BID and the dose of EIDD-2801 may be the same or lower than doses studied in previous Part(s), but not to exceed 800 mg BID.

The study parts will be conducted as follows: Part 1 of the study may be terminated upon approval and implementation of Protocol Amendment 3, and Part 2 will be initiated immediately thereafter. Part 3 will be initiated once Part 2 has been fully enrolled. If initiated, Part 4 may begin enrolling participants as soon as Part 3 has been fully enrolled. Study Parts 2 and 3 may be terminated prematurely based on emerging data from this and other ongoing studies of EIDD-2801.

On Day 1, participants will be assigned a unique ID number (randomization number). The randomization number encodes the participant's assignment to one of the groups of the study, according to a randomization schedule generated prior to the start of each individual study part. Each participant will be dispensed blinded study drug, labeled with his/her unique randomization number, throughout the study.

In case of an emergency, the investigator has the sole responsibility for determining if unblinding of a participants' study drug assignment is warranted. Participant safety must always be the first consideration in making such a determination. If the investigator decides that unblinding is warranted, the investigator should make every effort to contact the sponsor prior to unblinding a participant's study drug assignment unless this could delay emergency treatment of the participant. If a participant's study drug assignment is unblinded, the sponsor must be notified within 24 hours after breaking the blind. The date and reason that the blind was broken must be recorded in the source documentation and case report form, as applicable. If the investigator decides that unblinding is warranted, unblinding of a participant's study drug assignment will be coordinated by the unblinded pharmacist for the study.

Version: 7.0

4.3. Intervention

4.3.1. Screening

Adult patients who are newly hospitalized with PCR-confirmed SARS-CoV-2 and evidence of symptomatic COVID-19 will be invited to participate in the study. Those who express interest will undergo the informed consent process and be given the chance to ask any questions before agreeing to participate. Those who consent to participate will undergo screening for study entry; the time between screening and study entry should be as short as possible (ideally the same day, but no longer than 48 hours). Screening assessments will include demographics, medical history, concomitant medications, review of inclusion and exclusion criteria, height, weight, BMI, physical examination including vital signs, clinical chemistry labs (CMP), hematology (CBC with differential), high sensitivity serum betahuman chorionic gonadotropin (HCG) (to rule out pregnancy) as applicable, urinalysis, electrocardiogram (ECG), and pulse oximetry. It is expected that measurements/values will have been obtained as SOC, and medical chart extraction will be performed. Missing values will be obtained as part of study procedures. Any chest radiography results from hospital admission will be recorded.

4.3.2. Administration of Study Drugs

Upon completion of baseline assessments (including virologic assessments below), participants will then be administered the first dose of study drug (EIDD-2801 or placebo). Each participant will begin study treatment dosing with the first dose on the morning of Day 1, if possible. If the first dose is given later in the day, the second dose may be given at least 4 hours later on Day 1. Study drug administration will continue BID for a total of 5 days (10 doses). If the first dose on Day 1 is given in the late evening, the second dose may be taken on the morning of Day 2, in which case the final dose will be taken on the morning of Day 6.

In the event of missed doses, if the total number of missed doses is 4 or fewer, the number of days of study drug can be extended by no more than 1 day (through Day 6) with the equivalent of missed doses up to 2 doses. If the participant misses more than 4 consecutive doses, or more than 5 total doses, then the participant will be discontinued from any further study drug administration and followed for safety for the remainder of the study. Missed doses and times of administration will be recorded.

If a participant cannot ingest capsules orally during the study period, capsules will be opened, and the powder will be mixed with water and administered by mouth or through a nasogastric, percutaneous endoscopic gastrostomy (PEG) or orogastric tube.

4.3.3. Virologic Assessments

Upon enrollment, participants will have 2 NP swabs performed, one in each nostril (R or L to be documented), accessing the posterior nasopharynx. The NP swabs will be collected and stored separately for laboratory analysis. On Days 3, 5, 8, 11, 15 (inpatients only), 19 (inpatients only), and 28, participants will also have 2 NP swabs performed in the same way, collected and stored identically and individually. One swab will be sent to an infectivity lab for analysis. The other swab will be sent to for PCR sequencing. Detailed instructions for preparation and shipment of samples will be provided in a separate document.

Version: 7.0

Version: 7.0 18 May 2021

In the setting of bronchoalveolar fluid lavage with sampling, or in participants who require mechanical ventilation who have endotracheal tube fluid sampling, we will collect a portion to perform viral RNA testing and the infectivity assay on the sample. If available from SOC procedures, a sample of sputum will also be collected if the participant has a productive cough and used to perform viral RNA testing and infectivity assays. In addition, a portion of material from NP swabs will be archived and frozen for viral sequencing.

4.3.4. Clinical Assessments

On each day that virology samples are obtained, participants will be assessed for clinical endpoints and interim AEs (and SAEs). Chart review will occur on structured days to perform safety assessments and record concomitant medications (including antivirals). CMP, CBC with differential, and urinalysis will be recorded at regular intervals during the study as indicated in the Schedule of Events (see Section 7.1). Any results that are not available will be obtained on the applicable chart extraction day.

Participants who are discharged from the hospital during study participation will return to the clinic for study visits through the Day 28 visit. Clinic visits will occur on Days 3, 5, 8, 11, and 28. On Day 15 (± 1 day), a member of the study staff will contact the participant by telephone to query them about symptoms, study drug adherence, and concomitant medications. Outpatients will be seen in one of several locations, including but not limited to COVID-19 ambulatory pods, COVID-19 ambulatory clinics and clinical research units, and home visits. In all cases, visits will conform to infection control practices that are established by the institution. If the participant is discharged to a secondary care facility, study site staff will take measures to meet institutional regulatory requirements of the primary site as well as the receiving site to continue collecting study-related samples where allowed.

During in-clinic study visits, partial pressure of oxygen (PO2) will be measured by oximetry, and oral temperature will be documented. Other vital signs will be assessed, and a targeted physical examination will be conducted as needed. AEs and concomitant medications will be collected that have occurred since the last visit/report. Safety lab assessment (CBC with differential, CMP, and urinalysis) will be conducted, and for women of childbearing potential, a high sensitivity serum pregnancy test will be performed at the end-of-study (EOS) visit or at early discontinuation. Results of a single post-dose ECG should be recorded. If the participant is discharged from the hospital before a post-dose ECG is recorded, and recording of an outpatient ECG is not feasible, then results of the last recorded ECG before hospital discharged will be entered into the CRF. The results of any chest diagnostics done as part of SOC will be recorded. Any SAEs will be followed for 30 days after the end of study participation as detailed in Section 8.10.3.

Participants who are discharged from the hospital before the EOS visit will continue to take study drug at home for the full 5 day course, and drug accountability will be conducted at the Day 5 and/or Day 8 interim study visits, where allowed by the study institution. Participants will be instructed on how to report worsening of disease, including development of any additional symptoms of pneumonia or other concerning illness that may require interim assessment including clinic or urgent visits.

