1.2. Primary Safety Objective

Primary Safety Objective:

To evaluate the safety of treatment with EIDD-2801 in participants diagnosed with COVID-19

Primary Safety Endpoints:

- 1. Adverse events (AEs)
- 2. Serious adverse events (SAE)
- 3. Physical examination including vital signs
- 4. Safety laboratory assessments:
 - complete blood counts (CBC) with differentials
 - decrease in hemoglobin (Hgb) by >1 g/dL, or to <9 g/dL
 - decrease in platelet count by $50,000/\mu$ L, or to $<75,000/\mu$ L
 - comprehensive metabolic panels (CMP) including liver function tests
 - increase in aspartate aminotransferase (AST), alanine aminotransferase (ALT), amylase, or lipase to ≥3x the upper limit of normal (ULN)
 - urinalysis
- 5. Electrocardiograms (ECGs)

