4.8. Study Discontinuation

If a participant is withdrawn from the study, the reason for withdrawal and the date the participant was removed will be documented in the case report form (CRF). A participant must be discontinued from the trial for any of the following reasons:

- Version: 7.0 18 May 2021
- The participant or legal representative (such as legal guardian) withdraws consent.
- Intercurrent illness that prevents further administration of treatment.
- Severe or life-threatening EIDD-2801-related AE(s).
- If in the opinion of the Investigator, a change or temporary or permanent discontinuation of therapy would be in the best interest of the participant.
- Noncompliance with trial treatment or procedure requirements.
- Participant is lost to follow-up.
- Participant becomes pregnant.

If a randomized participant withdraws from the study and has not been administered a dose of study drug or placebo, they will be replaced. Additional participants may be randomized, if needed, to ensure that an adequate number of participants provide Day 5 efficacy data.

Whenever possible, participants should continue to be monitored for safety through the remainder of the study.

The investigator should make every effort to perform the assessments indicated for the End-of-Study visit (see the Schedule of Events; Section 7.1) for participants who discontinue early from the study.

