6.2.7. Analysis of Other Safety and Clinical Data

Other safety and clinical endpoints will be provided descriptively by dose group and scheduled time of assessment where appropriate. Details will be provided in the SAP.

Version: 7.0

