7. STUDY PROCEDURES

7.1. Schedule of Events

Inpatient											
Study Procedures	Screening ^a Day -2 to 1	Day 1	Day 3	Day 4	Day 5	Day 8	Day 11	Day 15	Day 19	Day 28 (EOS)	Early Discontin- uation
Informed Consent	X										
Demographic data	X										
Inclusion/Exclusion Criteria	X										
Randomization ^b		X									
Medical History	X										
Pregnancy test ^c	X									X	X
Serology (plasma) ^d		Xe			X				X		
Height, weight, BMI	X										
Study residency											
Visit while hospitalized for MR review	X	X	X		X	X	X	X	X	X	X
Prior/Concomitant medication review	X	X	X		X	X	X	X	X		
Study drug vs. placebo											
EIDD-2801 or PBO		BID on	BID on	BID on	BID on						
administration		Days 1-5	Days 1-5	Days 1-5	Days 1-5						
Virologic endpoints											
NP swabs ^g		Xe	X e		X e	X	X	X	X		
BAL and/or sputum ^h		X	X		X	X	X	X	X		
Clinical endpoints											
WHO Ordinal Scale (Appendix 1) ⁱ		Xi	X		X	X	X	X	X	X	X
Clinical assessments ^j		X	X		X	X	X	X	X	X	X
Safety and tolerability											
AE/SAE reporting		X	X		X	X	X	X	X	X	X
Vital signs (temperature, blood pressure, pulse, respiratory rate)	X	X	X		X	X	X	X	X	X	X
Pulse oximetry ^k	X	X	X		X	X	X	X	X	X	X
Full physical examination	X			1						X	
Targeted physical examination ¹		X	X		X	X	X	X	X		X
Laboratory ^m	X		X		X	X		X	X		

Inpatient											
Study Procedures	Screening ^a Day -2 to 1	Day 1	Day 3	Day 4	Day 5	Day 8	Day 11	Day 15	Day 19	Day 28 (EOS)	Early Discontin- uation
12-lead ECG ⁿ	X						1 1	osttreatme	nt ECG to 1	pe performed, as fe	asible ⁿ
Chest radiography ^o		X	X		X	X	X	X	X	X	X
Pharmacokinetics											
Plasma ^p			X	X		·					
PBMCs ^p			X	X							

Abbreviations: AE = adverse event; BAL = bronchoalveolar lavage; BID = twice daily; CBC = complete blood count; CMP = complete metabolic panel; ECG = electrocardiogram; EOS = end of study; h = hours; ICU = intensive care unit; IL-6 = interleukin 6;

MR = medical record; NP = nasopharyngeal; PBMC = peripheral blood mononuclear cell; PBO = placebo; PK = pharmacokinetic; QD = once daily; QOD = every other day; SARS-CoV-2 = severe acute respiratory syndrome-coronavirus-2; SOE = schedule of events; WHO = World Health Organization.

- a. Screening and Day 1 procedures will occur on the same day whenever possible as soon as SARS-CoV-2 testing is determined to be positive. A window of up to 6 days is allowable if the participant has not had symptoms for more than 7 days prior to dosing.
- b. Randomization can happen at Screening or Day 1

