- k. Oxygen saturation is to be recorded twice daily (morning and evening) and may be ascertained by chart extraction; if not available in the participant's chart, it should be measured by the study staff.
- 1. Targeted physical examinations should be done if indicated by an AE or as needed in the judgement of the investigator.
- m. Laboratory measurements will include CBC with differentials, CMP (including amylase and lipase), and urinalysis.
- n. For ECGs, a single post-dosing recording should be collected. If the participant is discharged from the hospital before a post-dose ECG is recorded, and recording of an outpatient ECG is not feasible, then results of the last recorded ECG before hospital discharge will be entered into the CRF.
- o. Results of all chest radiography performed as part of routine clinical care during Study Days 1-28 should be recorded.
- p. Plasma and PBMC samples for PK analysis will be collected from participants if they are still inpatients on Day 3. Samples will be collected before the morning dose on Day 3 and at the following times after the Day 3 morning dose: 0.5 hours, 1.5 hours, 3 hours, 6 hours, 8 hours, and 24 hours (i.e., on the morning of Day 4). If a participant is scheduled to be discharged, then PK samples should be collected at all scheduled time points up to the time of discharge; in addition, if a participants is discharged prior to the 24-hour PK sample, a 12-hour PK sample should be collected, when possible. PK measurements will be assessed in participants enrolled at clinical sites able to conduct the collections. These sites include, but are not limited to,
 - be collected within a \pm 15 minute window (up to 3 hours), \pm 30 minutes (6-8 hours), or \pm 1 hour (12-24 hours).

	Outpatient ^a						
Study Procedures	Day 3	Day 5 ^b	Day 8 (±1 day)	Day 11 (±1 day)	Day 15 (±1 day)	Day 28 (EOS) (±2 days)	Early Discontin- uation
Serology (plasma) ^c		X				X	X
Pregnancy test ^d						X	X
Study residency							
Outpatient visit	X	X	X	X		X	X
Phone call ^e					X		
Study drug vs. placebo							
EIDD-2801 or PBO administration ^f	BID on Days 1-5	BID on Days 1-5					
Virologic endpoints							
NP swabs ^{g, h}	X	X	X	X		X	X
Clinical endpoints							
WHO Ordinal Scale (Appendix 1) ^h	X	X	X	X	X	X	X
Safety and tolerability							
Concomitant medication review	X	X	X	X	X	X	X
AE/SAE reporting h	X	X	X	X	X	X	X
Vital signs (temperature, blood pressure, pulse, respiratory rate) h	X	X	X	X		X	X
Pulse oximetry ^j	X	X	X	X		X	X

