Targeted physical examination ^k	X	X	X	X		X	X
Laboratory ¹	X	X	X	X		X	X
Chest radiography ^m	X	X	X	X		X	X

Abbreviations: AE = adverse event; BAL = bronchoalveolar; BID = twice daily; CBC = complete blood count; CMP = complete metabolic panel; ECG = electrocardiogram; EOS = end of study; ICU = intensive care unit; IL-6 = interleukin 6;

; $MR = medical \ record$; NP = nasopharyngeal; PBO = placebo; PK = pharmacokinetic; $QD = once \ daily$; $QOD = every \ other \ day$; $SOE = schedule \ of \ events$; $WHO = World \ Health \ Organization$.

- a. For participants who are discharged from the hospital after randomization and administration of the first-dose of study drug or PBO, this schedule will apply. Day number will be counted from enrollment. Participants will enter the Outpatient SOE upon day of discharge. Outpatients will be seen in one of several locations, including but not limited to COVID-19 ambulatory pods, COVID-19 ambulatory clinics and clinical research units, and home visits. In all cases, visits will conform to infection control practices that are established by the institution.
- b. If Day 5 falls on a Saturday, then a visit will occur on Day 4. If Day 5 falls on a Sunday, then a visit will occur on Day 6.

- c. Serology testing will be performed on plasma for IL-6 levels on Day 1 (pre-dose), Day 5 and Day 28, and specimens will be archived for further cytokine testing in the future.
- d. Pregnancy test is required for women of childbearing potential only. High sensitivity serum pregnancy tests are required on Day 28. Additional serum or urine pregnancy tests may be performed, as determined necessary by the investigator or required by local regulation, to establish the absence of pregnancy at any time during the subject's participation in the study.
- e. Phone calls will be used to query participants about symptoms, study drug adherence, concomitant medications and to assess WHO ordinal scale.

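### After Day 8 the inpatient and outpatient schedules share no safety-laboratory day, so late by-visit comparisons of dose with placebo are confined to subsets defined by discharge

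*Protocol*

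**What the plan says.** Section 4.3.4 leaves the timing of the safety laboratory to the table in Section 7.1: "CMP, CBC with differential, and urinalysis will be recorded at regular intervals during the study as indicated in the Schedule of Events". The content is the same in both settings: "Laboratory measurements will include CBC with differentials, CMP (including amylase and lipase), and urinalysis". The marked days differ.

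- Inpatient Laboratory row: Screening and Days 3, 5, 8, 15 and 19. Day 11, Day 28 (end of study) and Early Discontinuation are blank.
- Outpatient Laboratory row: Days 3, 5, 8, 11, 28 and Early Discontinuation. Day 15 is a telephone contact and there is no Day 19 column. Section 4.3.4 agrees: "Clinic visits will occur on Days 3, 5, 8, 11, and 28".

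A participant moves from one schedule to the other at discharge: "Participants will enter the Outpatient SOE upon day of discharge".

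Laboratory thresholds are primary safety endpoints in Section 1.2, for example "decrease in hemoglobin (Hgb) by >1 g/dL, or to <9 g/dL", with others for platelets, transaminases, amylase and lipase. Section 6.2.7 gives the form of the summary: "Other safety and clinical endpoints will be provided descriptively by dose group and scheduled time of assessment where appropriate". Under Section 6.2.2, nominal visits are used without windows, and unscheduled visits are listed but kept out of the tables.

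For early discontinuers, Section 4.8 says: "The investigator should make every effort to perform the assessments indicated for the End-of-Study visit".

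**The concern.** Discharge happens after randomisation, and either drug effect or toxicity may change its timing. If it decides which late laboratory days a participant has, a late by-visit table no longer compares the randomised arms. It compares dose with placebo among those already discharged (Days 11 and 28) or among those still in hospital (Days 15 and 19). A difference, or the absence of one, could then reflect who is in the subset rather than the drug.

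For endpoints of the form *threshold ever crossed*, both schedules contribute, but participants are tested a different number of times and on different days. More tests give more chances to cross a threshold.

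The inpatient table also has no laboratory mark at the end of study or at early discontinuation, although Section 4.8 points early discontinuers to the end-of-study assessments.

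**Working it through.** The plan states no figure on this point, so there is none to reproduce. The check compares the two Laboratory rows cell by cell.

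**1. Column alignment.** The inpatient row has 11 cells for 11 column heads, and the outpatient row has 7 for 7. As a control, the inpatient pregnancy-test row read the same way falls at Screening, Day 28 and Early Discontinuation. Its footnote gives the first two and Section 4.3.4 gives the third. Inpatient rows such as vital signs, oximetry and the WHO scale do carry marks at Day 11, Day 28 and Early Discontinuation, so the blanks belong to the Laboratory row.

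**2. Shared days.** After Day 8 the inpatient set is {15, 19} and the outpatient set is {11, 28, Early Discontinuation}. The intersection is empty. The shared post-baseline days are 3, 5 and 8.

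**3. Tests by discharge day.** Assume one discharge, no readmission, follow-up to Day 28, and the outpatient schedule from the day of discharge onwards.

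| Discharged | Scheduled post-baseline laboratory days | Number | Longest late interval |
|---|---|---|---|
| By Day 11 | 3, 5, 8, 11, 28 | 5 | 28 − 11 = 17 days |
| Day 12 to 15 | 3, 5, 8, 28 | 4 | 28 − 8 = 20 days |
| Day 16 to 19 | 3, 5, 8, 15, 28 | 5 | 28 − 15 = 13 days |
| Day 20 to 28 | 3, 5, 8, 15, 19, 28 | 6 | 28 − 19 = 9 days |
| Still in hospital at Day 28 | 3, 5, 8, 15, 19 | 5 | no test in the last 28 − 19 = 9 days |

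**4. Size of the late tables.** Section 6.1 expects at least 14 participants in each higher-dose group and on placebo. Those with a Day 11 test were discharged by Day 11, and those with a Day 15 test are in hospital on Day 15. Nobody is in both groups. In an arm of 14 with k discharged by Day 11, the Day 11 table holds k and the Day 15 table at most 14 − k. Whatever k is, one of the two rests on 7 participants or fewer. The protocol gives no length of stay, so k cannot be fixed further.

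**5. Interim reviews.** Section 9.2 reviews safety once a set share of participants reach Day 14, using cumulative incidence by arm. By then a participant discharged by Day 11 has had 4 scheduled tests (Days 3, 5, 8, 11). One still in hospital on Day 11 has had 3 (Days 3, 5, 8).

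**6. Whether other text closes the gap.**
- Section 4.3.4 has unavailable results obtained on the chart-extraction day. That refers to results the schedule calls for, and the inpatient schedule calls for none on these days.
- A later sentence in Section 4.3.4 mentions safety laboratory tests together with the end-of-study or early-discontinuation pregnancy test. Its paragraph opens with in-clinic visits, so it may cover outpatients only. If it covers inpatients too, it contradicts the table.
- Section 4.8 leads an inpatient to an end-of-study column whose laboratory cell is blank.
- Section 6.2.2 prevents Day 11 and Day 15 results from being brought together by windows, and keeps results from unscheduled visits out of the tables.

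**The case against.** The strongest reply is that this is a narrow gap in late descriptive tables. Dosing ends on Day 5 or 6 (Section 4.3.2), and Days 3, 5 and 8 are common to both settings, so the period of exposure and shortly after is covered for everyone. By-visit summaries apply where appropriate, with details left to an analysis plan that is not at hand, and cumulative threshold endpoints pool both schedules. All of that stands and limits the point to later laboratory data. It does not remove the point: an analysis plan cannot tabulate tests that were never scheduled, and pooling leaves the number and timing of tests unequal.

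Three stronger readings are tempting and are not supported.

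- *A reader might infer that toxicity is compared between discharged and hospitalised participants.* The contrast remains dose group against placebo. It is restricted to a subset, not replaced.
- *A reader might infer that an inpatient withdrawn for a severe event has no laboratory follow-up.* Section 8.10.2 makes worsening grade 3 and 4 results, and any abnormality that leads to stopping the study product, reportable as adverse events. Sections 8.10.1 and 8.10.3 require follow-up. What is missing is a scheduled test. Adverse event reporting also does not replace the threshold endpoints: grade 1 and 2 results are reported only if judged clinically significant, while the thresholds are numeric.
- *A reader might infer that added antivirals are missed because the inpatient row* "Prior/Concomitant medication review" *stops at Day 19.* Section 4.3.4 has chart review record concomitant medication, antivirals included, and the inpatient record-review row is marked at Day 28 and Early Discontinuation.

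The Day 28 gap also does not affect everyone who was ill for long. Anyone discharged before then has a Day 28 test on the outpatient schedule. It concerns only those still in hospital.

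**Conclusion.** The point holds for laboratory safety data after Day 8. Of the four later laboratory days (11, 15, 19, 28), none is common to both settings. The number of scheduled post-baseline tests runs from 4 to 6, and the longest interval without one reaches 20 days for a participant discharged between Day 12 and Day 15. Participants in hospital at Day 28 or at early discontinuation have no laboratory test marked, and Sections 4.3.4, 4.8 and 7.1 do not agree clearly on whether they should.

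This rests on the table as read, one discharge per participant, and the no-window rule of Section 6.2.2. How many participants each late table would hold depends on length of stay, which the protocol does not give. It is a worthwhile and cheap improvement to a primary safety endpoint. It does not undermine the safety data collected during dosing.

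**What to change.** In the inpatient schedule of Section 7.1, mark Laboratory at Day 11, Day 28 and Early Discontinuation, to match the outpatient schedule. State in Sections 4.3.4 and 4.8 that safety laboratory tests at the end of study and at early discontinuation apply in both settings. Use Days 3, 5, 8, 11 and 28 as the common time points for by-arm summaries, and present Days 15 and 19 as supplementary inpatient data.

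Every participant followed to Day 28 would then share five post-baseline laboratory days, against three now. Those discharged after Day 15 or still in hospital would have 6 or 7 tests in all, so threshold summaries should also be shown on the five common days alone, which makes the number of tests equal. The 17-day interval from Day 11 to Day 28 for discharged participants would remain.

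The cost is three marks in one table, a sentence in each of two sections, and a few extra chart extractions or blood draws in participants still in hospital. Record-review visits are already scheduled for them on Day 11, Day 28 and at early discontinuation.
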